7.2.2. Observational Studies Monitoring Board (OSMB)

Yearly data reports are prepared by the GIC and provided to the OSMB for review. In addition to the material provided in the monthly management reports, data summaries integral to the ability of the study to address its primary objectives are included.

7.3. Analysis Plan

Data analyses will be conducted in SPIROMICS with the overarching goal of achieving the two primary study objectives, namely, the identification of homogenous subgroups of COPD patients and the identification of potentially useful intermediate outcomes, both of which can inform future therapeutic clinical trials with an emphasis on trials conducted for regulatory approval. The data planned for collection in SPIROMICS are extensive and involve fairly complex data structures. Numerous specific hypotheses directed at both general study aims will be evaluated. Detailed statistical analysis plans will be developed for each specific hypothesis describing the methods to be used for data analysis and addressing issues such as missing data and multiplicity of statistical testing.

Hypothesis # 1 -- Subgroup Identification: Three different approaches will be taken to subgroup finding. The first assumes that homogeneous subgroups can be defined in terms of multiple measurement domains (including clinical, radiological, proteomic, and genomic) through the application of statistical techniques, such as hierarchical cluster analysis, described in Sections 7.4.1 and 7.4.2. Discovery of novel clustering or classification schemes is the goal of analyses conducted with this approach, therefore it is difficult to specify a priori hypotheses to be evaluated. Examples, however, can be provided, such as:

- Clusters of participants will be defined based on genome-wide genetic, epigenetic, and gene expression data that share molecular pathways of disease and are therefore useful in guiding development of targeted therapeutic approaches.
- Homogeneous subgroups of patients will be identified according to their ‘sputum footprint,’ defined as mucin concentration, microbiome content, and neutrophil concentration, that will provide novel groupings of disease severity and therefore be useful for targeted enrollment in future clinical trials.

Because this approach involves discovery of novel subgroups rather than confirmation of a priori hypothesized subgroups, cross-validation methods to assess the predictive power of a particular subgroup classification scheme will be invoked.

The second approach to subgroup finding posits that individualized therapies based upon a patient’s genotype are possible. DNA collection followed by either genome-wide association or specific genetic tests combined with statistical analyses will allow us to evaluate this hypothesis and to continue to unravel the correlation between underlying genetics and resultant phenotypes. Several genes have been recently reported to be associated with COPD phenotypes (see, e.g., Wood, Tan, and Stocklye, 2009 *Genome Medicine* 1:112). Concurrently run studies (e.g., the COPDGene Study (COPDGene Investigators, 2010)) will add to this list, and SPIROMICS will

be valuable in validating newly emergent findings from these studies. An example of a specific hypothesis under this approach is:

- SPIROMICS participants with SNPs previously associated with FEV₁ decline (CHRNA3/5, EPHX1, GSTP1, and HHIP) will have faster rates of decline in FEV₁ over three years than participants without those SNPs.

The third approach to subgroup finding suggests that components of COPD syndrome can be prospectively identified that are associated with a worse prognosis, as measured by morbidity over a 3-year period, when compared to participants without those components. There are many specific examples of this general hypothesis, including the following:

- Participants with apical emphysema at baseline will have more exacerbations resulting in a hospitalization over three years than those without apical emphysema.

Hypothesis #2 – Intermediate Outcome Identification: This general hypothesis can more specifically be stated as: SPIROMICS will identify intermediate outcome measures that predict long-term clinical endpoints of morbidity. Such outcomes may be markers of short-term change (1 year) that predict long-term change (3 years), or they may be markers that change with exacerbations and are predictive of more severe long-term morbidity/mortality.

For example:

- The novel molecular methodologies employed in SPIROMICS (including T-RFLP, phylochips, and deep-sequencing) will provide candidate markers that correlate with more frequent exacerbations and are therefore predictive of long-term morbidity/mortality.

Both Hypotheses #1 and #2 (and subsequent examples) are longitudinal, and therefore differentiate SPIROMICS from other studies that are purely cross-sectional studies. They are currently viewed as co-primary hypotheses. The statistical methods planned to address these and other hypotheses are described in detail in the follow subsections.

7.4. Statistical Methods

7.4.1. Phenotype Identification for Subgroup Analyses

The SPIROMICS study will gather data from a variety of measurement domains, yielding a very large number of observations per patient. Subgroups may be defined in terms of multiple measurements, including clinical, proteomic, genomic, and radiological measurements plus combinations thereof. To identify subgroups, we will initially examine the data without regard to study design strata or clinical endpoints. Therefore no testing multiplicity issues will arise, and a variety of statistical methods can be used to examine the data for evidence of cohesive groups for which the within-group variation is smaller than the overall variation. Continuous measurements will first be regressed on covariates such as age, gender, height, and weight and design stratum to obtain residuals, which will be carried forward into the subgroup analyses. The rationale for including design stratum as a predictor is that we do not wish to recapitulate subgroups that are essentially equivalent to strata that can already be used for future trial design.

As the model-based residuals involve only the use of main stratum effects, the identified subgroups may still be correlated with the design strata.

A variety of subgroup identification procedures are described in the subsection below. Each subgroup type will be described in terms of a “cohesiveness index,” which is essentially a global description of the proportion of variation in the constituent measurements that is explained by the subgroup variable. Once cohesive subgroups have been identified, each patient will be assigned to a unique subgroup, using the appropriate distance metric for the subgroup identification procedure. For subgroup identification, we conceptually distinguish between subgroups that (i) do not correlate with study design stratum/COPD severity or with clinical endpoints, but which nonetheless may be predictive of treatment response in future clinical trials, and (ii) subgroups that do correlate with strata and/or clinical endpoints. We anticipate that the most useful subgroups are likely to be at least modestly associated with design strata and/or clinical endpoints, and so we will use such associations to further prioritize the set of potentially useful subgroups. The subgroup indicators will be tested for associations with the 4-strata design indicators using $k \times 4$ contingency table analysis. In addition, ordered logistic regression modeling will be performed, with design strata ordered as Non-smokers, Smokers, Mild/Moderate COPD, Severe COPD, and the subgroup indicators as predictors. Note that multiple types of subgroups may be fit in the same model, potentially with interaction terms to identify potent combinations of subgroups of different types (e.g. a particular combination of genomic and radiological measurements). Regression procedures will also be used to identify subgroup indicators that correlate with clinical endpoints, including mortality (proportional hazards regression), exacerbations (Poisson regression), and decline in FEV₁ (linear regression).

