2.1.3. Exacerbations in COPD

[figure not shown]
Exacerbations, which are defined by the GOLD document as "an event in the natural course of the disease characterized by a change in the patient's baseline dyspnea, cough, or sputum that is beyond normal day-to-day variations, is acute in onset, and may warrant a change in regular medication," are of extreme importance in clinical management of COPD (GOLD Executive Committee, 2008). Exacerbations have a profound effect on the patient, and they contribute significantly to the overall morbidity and mortality associated with this disease (Anzueto 2010; Niewowhner 2006). Exacerbations are often associated with worsening airflow obstruction and can result in more rapid decline in lung function, increased peripheral muscle weakness, and decreased quality of life. Patients with frequent exacerbations have a reduced quality of life and increased mortality. It is now accepted that during an exacerbation, increased inflammation both in the lungs and the systemic circulation can affect many organs and systems. Numerous abnormalities can be found outside the lungs during and after an exacerbation that affect nutritional status, skeletal muscle function, and bone mass as well as the cardiovascular and endocrine systems. Thus, prevention and treatment of exacerbations are major objectives in the clinical management of COPD.

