7.1. Sample Size and Power

Thirty-two hundred (3,200) participants will be recruited and enrolled at six clinical centers into four strata (non-smokers, smokers, mild/moderate COPD, severe COPD) as illustrated in Table 1. The sample size requirements for the study are to (1) provide an adequate number of adverse clinical events (e.g., exacerbations, all-cause mortality) over three years of follow-up and (2) sufficient precision in estimating decline in FEV₁ over three years of follow-up in order to support the study objectives of discovering novel, homogeneous subgroups of COPD and identifying potentially useful, intermediate outcomes of disease progression.

Table 1. SPIROMICS Enrollment Strata

	Non-Smokers (Stratum 1)	Smokers (Stratum 2)	Mild/Moderate COPD (Stratum 3)	Severe COPD (Stratum 4)
Smoking Status	< 1 pack-year	> 20 pack-years	> 20 pack-years	> 20 pack-years
Bronchodilator Status for Assessing Lung Function	Pre- bronchodilator	Post- bronchodilator	Post- bronchodilator	Post-bronchodilator
FEV1/FVC ratio criteria	FEV1/FVC > .7	FEV1/FVC > .7	FEV1/FVC < .7	FEV1/FVC < .7
Other Lung Function Criteria	FVC>LLN	FVC>LLN	FEV1 > 50% pred.	FEV1 < 50% pred.
Sample Size	N = 200 (6.25%)	N = 900 (28.13%)	N = 1500 (46.88%)	N = 600 (18.72%)

Data on event rates for all-cause mortality in the COPD population are available from the TORCH study, a clinical trial comparing salmeterol plus fluticasone propionate versus placebo and each therapy alone over a three-year period (Calverley, et al., 2007). Below we use the TORCH results to provide a lower bound on plausible differences between hypothetical subgroups of COPD patients with respect to morbidity/mortality for purposes of estimating power. In addition, where possible, estimates of FEV₁ change over time are derived from published findings for power analyses. Estimates of the power available for comparisons of the Mild/Moderate versus Severe COPD enrollment strata are provided for illustration purposes, as sizes of novel subgroups yet to be discovered are unknown at this time. All statistical tests will be two-sided, with Type I error alpha=0.05 after controlling for multiple testing.

For the TORCH study, all-cause, three-year mortality rates ranged from 15.2% among placebo patients to 12.6% in the combination therapy group. Results from Anthonisen et al. (1986) found

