that the three-year mortality was approximately 25% for patients with FEV₁ in the range 30%-39% , and approximately 13% for those with FEV₁>50%. More recently Celli et al. (2004) reported approximately 18% three-year mortality for patients with FEV₁>36% and 30% for patients with FEV₁<36%. We conservatively power the SPIROMICS study to detect a difference in all-cause mortality, assuming a 15% rate for Severe patients versus 10% for Mild/Moderate patients. With 1,500 patients in the Mild/Moderate COPD stratum vs. 600 patients in the Severe COPD stratum, we will have 88% power for this comparison.

For the TORCH study, the annual rate of exacerbations was 1.13 per participant for placebo versus 0.85 for combination therapy. In a computer model of COPD progression based on literature surveys, Borg et al. (2004) assumed an average annual rate of moderate to severe exacerbations of approximately 1.05 among COPD patients with GOLD status I/II, and a rate of 2.05 for exacerbations among COPD patients with GOLD status III. We conservatively power the SPIROMICS study to detect a difference in annual exacerbation frequency between the Mild/Moderate and Severe COPD strata, assuming an annual rate of 1.0 in the Mild/Moderate COPD stratum vs. a rate of 1.5 in the Severe COPD stratum. Using simulation and assuming a simple Poisson log-likelihood ratio test for difference in individual counts of exacerbations in the two strata and assuming 92% retention in both strata, we obtain power in excess of 95% to detect the differences.

For decline in FEV₁, the TORCH study found differences in change from baseline FEV₁ values of 0.092 (L) between the combination therapy group and placebo (95% CI = [0.075, .108]) (Calverley et al, 2007). With the proposed disease severity subgroup sample sizes and assuming attrition due to mortality ranging from 10% in the Mild/Moderate stratum to 15% in the Severe stratum, and 92% retention in those surviving in each strata, we would have approximately 95% power to detect a difference of 0.20 times the standard deviation in FEV₁ change from baseline values (using a two-sample t-test on baseline vs. Year 3 FEV₁ in the two strata).

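### Section 7.4.1 names Poisson regression for exacerbation counts without allowing for over-dispersion, so subgroup associations may be declared too readily

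*Protocol*

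**What the plan says.** Section 7.4.1 sets out how subgroups, once found, are tested against clinical endpoints. The procedures are listed by endpoint, "including mortality (proportional hazards regression), exacerbations (Poisson regression), and decline in" FEV₁, the last by linear regression. The associations found are used to rank the candidate subgroups.

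Section 7.1 powers the exacerbation endpoint by simulation with a "simple Poisson log-likelihood ratio test for difference in individual counts of exacerbations in the two strata and assuming 92% retention in both strata", "assuming an annual rate of 1.0 in the Mild/Moderate COPD stratum vs. a rate of 1.5 in the Severe COPD stratum", and reports power above 95%. The group sizes appear in the mortality calculation of the same section: "With 1,500 patients in the Mild/Moderate COPD stratum vs. 600 patients in the Severe COPD stratum". On error control, 7.1 says: "All statistical tests will be two-sided, with Type I error alpha=0.05 after controlling for multiple testing".

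The protocol does not treat patients as alike in exacerbation rate. Section 2.1.3 states: "Patients with frequent exacerbations have a reduced quality of life and increased mortality". Section 4.2.4 proposes that certain microbes may predict exacerbation rate. Section 7.1 cites literature rates of 1.05 per year for GOLD I/II and 2.05 for GOLD III. The terms over-dispersion, negative binomial, quasi-Poisson and robust variance do not occur in the protocol.

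**The concern.** Poisson regression with its usual standard errors assumes that patients with the same covariates share one event rate, so that the variance equals the mean. This study looks for heterogeneity that is not yet understood. Any proneness to exacerbation that the fitted indicators do not explain becomes extra variance, and the Poisson standard error ignores it.

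Section 7.4.3 lists exacerbations among the three primary clinical endpoints. The 7.4.1 regressions decide in part which subgroups move forward, and several types of subgroup may be tested. If the standard errors are too small, some subgroups will be promoted on chance associations and may be suggested for enrolment in later trials. A multiplicity correction does not help, because it acts on p-values that are already too small.

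**Working it through.** **Inputs.** From section 7.1: 1,500 and 600 patients, 92% retention, annual rates 1.0 and 1.5, two-sided alpha 0.05, three years of follow-up. Retained patients: 1,500 × 0.92 = 1,380 and 600 × 0.92 = 552. Mean counts: μ = 1.0 × 3 = 3.0 and 1.5 × 3 = 4.5. The dispersion k (variance = μ + kμ²) is an assumption, shown over a range.

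**1. The plan's own figure.** A simulated Poisson likelihood ratio test (20,000 replicates, 1,380 against 552) gives power of about 100% over one or three years. This agrees with the stated figure of more than 95%.

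With over-dispersion, SE(log rate ratio) = sqrt[(1/3 + k)/1380 + (1/4.5 + k)/552] and z = ln(1.5)/SE:
- k = 0: z = 0.405/0.0254 = 16.0
- k = 2: z = 0.405/0.0756 = 5.4

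Both are far above 1.96. Simulated negative binomial power is still 99.7% at k = 2 with only one year of follow-up. The power statement is sound.

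**2. Type I error of the Poisson test.** The true standard error is sqrt(1 + kμ) times the Poisson one, so the actual level of a nominal 5% test is 2 × [1 − Φ(1.96 / sqrt(1 + kμ))].

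| k | SE factor, μ = 3 | Actual level, μ = 3 | Actual level, μ = 4.5 |
|---|---|---|---|
| 0.1 | 1.14 | 8.6% | 10% |
| 0.25 | 1.32 | 14% | 18% |
| 0.5 | 1.58 | 22% | 28% |
| 1.0 | 2.00 | 33% | 40% |

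At μ = 3, doubling of the error rate needs k of about 0.14 and tripling needs about 0.28.

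**3. Check by model fitting.** A null 50/50 subgroup indicator, adjusted for stratum, was fitted to 1,932 simulated patients (1,000 fits per k, Monte Carlo error about 0.007 at the 5% level). The negative binomial fits used the true k.

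| k | Poisson | Robust | Quasi-Poisson | Negative binomial |
|---|---|---|---|---|
| 0 | 0.061 | 0.060 | 0.059 | 0.061 |
| 0.25 | 0.137 | 0.049 | 0.051 | 0.046 |
| 0.5 | 0.240 | 0.052 | 0.057 | 0.053 |
| 1.0 | 0.336 | 0.051 | 0.053 | 0.047 |

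This agrees with the formula, and each alternative restores the nominal level.

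**4. Stricter thresholds.** At a nominal 0.001, the level 7.1 uses for surrogate tests, the actual level at μ = 3 is 0.013, 0.037 and 0.100 for k = 0.25, 0.5 and 1.0.

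**5. Rarer events.** One example hypothesis in section 7.3 concerns exacerbations leading to hospitalisation. Assuming 0.2 per year (not in the documents), μ = 0.6 and the actual level is about 7%, 9% and 12% for k = 0.25, 0.5 and 1.0.

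**The case against.** The best reply is that 7.4.1 names a model family in a short list and fixes no variance estimator or offset for any endpoint. Poisson regression with a sandwich variance is still Poisson regression, and section 7.3 promises detailed analysis plans for each hypothesis. This has weight: the text does not rule out a correct analysis. But 7.3 does not qualify the Poisson choice, and the only other mention, in 7.1, is a "assuming a simple Poisson log-likelihood ratio test for difference in individual counts of exacerbations in the two strata". Read as it stands, the plan points to the ordinary model.

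A second reply is that resampling protects the results. The protocol states permutation or bootstrap for -omics and SNP analyses (7.4.2) and permutation for intermediate-outcome screening (7.4.3). It does not extend them to the endpoint regressions of 7.4.1. Section 7.3 does plan cross-validation of subgroup schemes, which gives some protection later.

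A third reply is that these regressions rank subgroups and confirm nothing. That is true, and it limits the harm.

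Three stronger readings are tempting, and the documents do not support them:
- **The false-positive rate is several-fold too high as a matter of fact.** A threefold rise needs k of about 0.28 or more at a mean of 3, and the documents give no k. At k = 0.1 the rise is 1.7-fold.
- **Follow-up time will be ignored, so early deaths look like low exacerbators.** Section 7.4.1 is silent on an offset and does not exclude one. The wording about individual counts belongs to the power simulation, which states its effect as annual rates. The 10% to 15% mortality attrition in 7.1 is applied to the FEV₁ calculation.
- **The power statement is wrong.** It reproduces, and it survives strong over-dispersion.

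**Conclusion.** The concern holds in a conditional form. Section 7.4.1 names Poisson regression for exacerbations with no allowance for over-dispersion, in a protocol that expects patients to differ in exacerbation rate. The direction of the error is certain if such variation remains within the model and model-based standard errors are used. Its size rests on the assumed k and on the mean count: from under twofold (k below about 0.14) to about 6.5-fold (k = 1.0) at three events per patient, and less for rarer events. The damage is confined to subgroup prioritisation and to confidence intervals that are too narrow. It should be fixed, but the study's validity does not depend on it.

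**What to change.** In section 7.4.1, replace the Poisson entry for exacerbations by negative binomial regression, or by Poisson regression with a robust (sandwich) variance. In the same sentence, state log follow-up time as the offset, so that the handling of unequal follow-up is explicit.

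The cost is one sentence. No more patients are needed, and the power statement in 7.1 can stay. Where counts are over-dispersed, confidence intervals will be wider by the factor sqrt(1 + kμ), which is their correct width. Where they are not, the simulation at k = 0 shows practically the same rejection rate for all methods.

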7.4.1.1. Subgroup Identification Procedures

Subgroup identification procedures will proceed under the assumption that most univariate clinical measurements have already been examined for potential correlation with outcome and potential utility in trial design. However, the utility of ensembles of measurements, along with new genomic and radiological measurements, is unknown. Thus we will proceed with techniques that are designed for high-dimensional settings, initially performing subgroup identification only within measurement “type” (e.g. clinical).

A basic tool for subgroup identification is hierarchical cluster analysis, for which we will perform agglomerative clustering using average linkage and correlation metrics. The identification of significant clusters (i.e. subgroups) can be a difficult task, although for parametric Gaussian cluster analysis the use of criteria such as Akaike Information can be used to determine the number of clusters when the sample size exceeds the number of observations. Bayesian approaches can also be used here, with probability-based model selection techniques and Bayes factors used to distinguish between models with different cluster sizes. Recently the SigClust procedure (2008) has been introduced for testing for cluster significance when the number of observations exceeds the sample size, and we will apply the procedure for high-dimensional measurement types.

A second technique is principal component analysis, which (for mean centered data) essentially follows from singular value decomposition of the data matrices. The use of principal

components to identify subgroups and control for stratification is a mature area in genomic analysis, and we will use similar ideas in SPIROMICS. A key aspect of principal components analysis lies in testing the significance of eigenvalues, and we will use the approach detailed in Patterson et al. (2006) to consider the number of eigenvectors/PCs that should be considered in subgroup identification.

As an adjunct to subgroup identification, we will also examine the various baseline measurements to attempt direct prediction of clinical endpoints, with design strata included as covariates. Although such procedures may not immediately identify the important patient subgroups, they will provide a list of measurements that may be further examined for defining and refining subgroups. The prediction techniques that will be used will include principal components regression, support vector machines, and penalized regression (LASSO and ridge regression). Prediction accuracy will be assessed by doing repeated 10-fold cross-validation using a large number of random data splits. The relative importance of individual measurements (as predictors) will be assessed by the proportion of cross-validation sets in which the predictor appears (for techniques which include variable selection), or by the average standardized coefficient across the cross-validation sets. Sets of important measurements will be further analyzed for evidence of subgroups, and considered in combination with previously identified subgroups.

